### **Contraception**

During the enrollment visit, a serum HCG test is conducted on female patients of fertile age. Women of fertile age must use safe contraceptive products, as recommended by the Clinical Trials Facilitation Group (CTFG).

Contraceptive products considered safe are: intrauterine devices or hormonal contraception (oral contraceptive pills, implants, transdermal patches, vaginal rings or long-acting injections) or if the patient practices sexual abstinence. They must be used during the whole duration of the trial (until day 30 in Phase I of the trial, and day 37 in Phase II of the trial). Subjects that are sterilized or infertile, are exempt from contraceptive use. This includes: patients that have undergone surgical sterilization (vasectomy, bilateral salpingectomy, hysterectomy, bilateral oophorectomy), or patients postmenopausal defined as no menstruation for 12 months or more prior to inclusion in the trial.

Unless a female patient is suspected of having become pregnant during the trial, no further pregnancy testing is conducted.

In men, there is no evidence of GM-CSF or the administered antibiotics increasing risk for human teratogenicity or fetotoxicity in early pregnancy. There are no data on the concentration of GM-CSF in the seminal fluid after GM-CSF administration in the pouch. There are also no data on potential subsequent exposure to a sexual partner through seminal fluid, but it is theoretically possible that a certain systemic concentration of GM-CSF can be achieved. Therefore, we recommend that male patients use a condom during the duration of the trial (until day 30 in Phase I and day 37 in Phase II).

There are no populations exempt from using the above-mentioned methods.

### Subsequent studies

Patients that leave or terminate the trial can participate in subsequent studies and or treatment with the study medicine, if they still meet inclusion and exclusion criteria at time of enrollment.

## 6. Study intervention

### Composition of the combined medication

A single dose of the medication will consist of 50 µg of molgramostim (non-glycosylated recombinant human GM-CSF produced in *E. coli*), 400 mg of fosfomycin disodium neutralized with succinic acid and 100 mg of metronidazole.

In this study, patients are administered the study drugs as a solution containing 50 µg of molgramostim, 400 mg of fosfomycin and 100 mg of metronidazole, first sprayed endoscopically in the pouch in the Phase I study, and then given as an enema in the Phase II study.

The medication is combined on-site by the principal investigator with 0.2 ml molgramostim intraintestinal solution (from 1.2 ml molgramostim 250 µg/ml) in low acyl Kelcogel CG-LA 0.25% (from CPKelco) and 100 mg metronidazole (from B. Braun i.v. solution 5 mg/ml solution in 100 ml) and 400 mg fosfomycin (from i.v. Infectofos 2 g) in sterile water with 0.25% calcium chloride (see appendix 10). Components A (molgramostim) and B (fosfomycin and metronidazole) are given subsequently into the pouch, they are therefore only combined *in situ*, not prior to administration. The 0.25% calcium chloride solution and Kelcogel 0.25% (gellan gum) are both inactive substances that, when combined, become an adhesive gel, that will possibly lower the risk of the patient immediately defecating (and thereby keeping the medicine in the pouch for a longer time to ensure exposure of the inflamed mucosa to the study medication).

The administration of fosfomycin and metronidazole with Kelcogel 0.25% and calcium chloride has previously been approved by the Danish Medicines Association (Reg.-no.: 2019-000131-51) in the MeFo-trial for application in the colon. Here, the investigator combined the two antibiotics with calcium chloride 0.25% immediately before application and this was given with kelcogel 0.25% through an endoscope to become an adhesive gel.

The general dosage guideline for adults treated with fosfomycin infusions is 12-24 g intravenously per day, divided onto 2 to 3 dosages. In those with impaired renal function and a glomerular filtration rate under 40 ml/minute dosages should be lowered. As we are only administering 400 mg of fosfomycin daily, we do not expect the need for lowering the dosage in patients with renal impairment. However, to ensure optimum safety of our trial participants, we will exclude patients with a eGFR < 40 ml/min from participating in this trial.

The general dosage guideline for treatment with metronidazole is 1500 mg intravenously per day. We are using much lower dosages in this study, 100 mg of metronidazole, applied topically in the pouch.

The general dosage guideline for treatment with GM-CSF in chemotherapy-induced neutropenia is a maximum of 10 µg/kg/day for 7-10 days, which is a much higher dosage than we will be using in this study.

### **Formulation, packaging and labeling, and acquisition**

Molgramostim, which is a water-soluble, non-glycosylated rhGM-CSF (recombinant human granulocyte-macrophage colony-stimulating factor) produced under GMP (Good Manufacturing Practice) rules in a strain of *E. coli* bearing a genetically engineered plasmid which contains a human GM-CSF cDNA (complementary deoxyribonucleic acid) coding sequence. The product is purified through a series of tested methods to remove process-related impurities. According to the ATC classification (Anatomical Therapeutic Chemical classification), GM-CSF belongs to the class L Antineoplastic and immunomodulating agents; L03 Immunostimulants; L03a Immunostimulants; and L03AA Colony stimulating factors. This results in the ATC code L03AA03 for molgramostim.

Repomol, for intrainestinal administration, contains molgramostim formulated in a solution at pH 7.0-7.4. The drug product must be stored at 2-8 °C. Repomol used in this trial is supplied by Reponex Pharmaceuticals A/S, Hørsholm, Denmark. The manufacturer is responsible for the study drug, including the packaging.

Fosfomycin (Infectofos, from Infectopharm) is a marketed medicine, used routinely in the surgical department of the study site. 1 vial contains 2 grams of fosfomycin in powder form, designed to be dissolved in either sterile water or isotonic glucose. Every box contains 10 vials of Infectofos. When dissolved, Infectofos has a pH 7-8. The drug is supplied by Unimedica Pharma ([name]).

Metronidazole (Metronidazole 'B. Braun'), is a marketed medicine, used routinely in the surgical department of the study site. 1 container consists of 500 milligrams of metronidazole in a soluble form, that can be diluted in either isotonic saline or isotonic glucose. The drug is supplied by B. Braun Medical ([name]).

The application of the medicine and the dose is recorded in the CRF (see appendix 4).

### **Product storage and stability**

Repomol is delivered by Reponex pharmaceuticals A/S, and received at the study site by the principal investigator according to the Good Clinical Practice guidelines for extended recipient control.

Repomol is provided in a 1.2-ml vial. Repomol must be stored in a refrigerator at 2-8°C in the original package, and must be protected from light. The temperature will be monitored by a temperature log.

The solution must not be frozen. Each vial contains 1.2 ml of Repomol containing a total of 300 µg molgramostim, the concentration of which is 250 µg/ml. The expiry date is indicated on each vial. The 1.2 ml vials each bear a label with relevant information e.g. identification name, batch number, expiry date and will be clearly marked as a trial drug. Each vial will only be used for application of the study drug for one patient. Administration and maintenance procedures will be outlined in detailed instructions before the administration of the first dose of Repomol.

Fosfomycin (Infectofos) should be kept at room temperature (between 15-30°C) away from excess heat.

Metronidazol (Metronidazol 'B. Braun') should be kept at room temperature (between 15-30°C) in a container in the original box to protect it from light.

### **Dosage, preparation and administration of the study drug**

The drug combination will be applied endoscopically as a spray and in the form of an enema, in Phase I and II respectively. The drug combination will be administered at the hospital by the investigator to ensure the correct concentration and dosage of the study drug.

Only designated staff will be allowed to handle and administer the study drug in the hospital. The study drug Repomol will be taken out of refrigerated storage approximately 10-30 minutes before use. An information sheet with clear instructions will be provided to guide the study staff.

Repomol is in a vial of 1.2 ml containing 300 micrograms of molgramostim. Of this, 0.2 ml (containing 50 micrograms of molgramostim) are administered to the patient.

One vial with 2g fosfomycin powder is dissolved in 100 ml metronidazole (5 mg/ml) and 25 ml calcium chloride giving a total volume of 125 ml of which 25 ml are administered to the patient (400 mg fosfomycin and 100 mg metronidazole in 25 ml calcium chloride 0,25%)

#### **Assessment of patient compliance with study drug**

During Phase I of the study, the application of the drug is done endoscopically as a spray. Therefore, correct application is confirmed visually. During Phase II of the study, the patient gets the first dosage of the drug in the outpatient clinic, with the investigator ensuring that application is done correctly. The daily application of the study drug on day 2-7 will also be in the hospital to ensure the correct dosage and compliance.

#### **Therapeutic endoscopy Phase I and II**

In this study, endoscopy of the pouch only is needed, which does not require a full bowel preparation. Instead, the patient can self-administer an enema (e.g. Microlax, containing sodium citrate and sodium laurylsulfoacetate) 1 hour before the examination. Visual assessment of the pouch mucosa will be performed, and biopsies of the pouch will be taken to assess the mucosa according to the PDAI, as well as to examine the microbial diversity. Biopsy size will be 2 mm with regular biopsy forceps, and 2 biopsies will be taken for histology and 2 of these for microbiology assessment.

The endoscopy of the pouch will be performed by a trained specialist surgeon or gastroenterologist in the outpatient endoscopy clinic.

## **7. Study schedule**

See Appendix 2 for schedule of events

#### **Screening**

Recruitment of patients will be done consecutively in the outpatient clinic. All patients with a flare up of acute pouchitis will receive information about the trial in the outpatient clinic and referred to the principal investigator. The treating physician, an experienced gastroenterologist on pouchitis, will only inform the patient that a clinical trial is ongoing, and give written information on the trial to the patient. If the patient is interested in hearing more about the trial, he or she will be offered a consultation with the principal investigator. Initial information and a consultation with the principal investigator therefore takes place before informed written consent. The identity of the patient and basic demographic information is given to the investigator after verbal consent from the patient in the outpatient clinic.

#### **Enrollment/Baseline**

Patients eligible for the study are offered a consultation with the principal investigator, and are informed about their right to bring a bystander along to this consultation. During this consultation, the patient will receive information about the trial. Afterwards, the patient will be offered the therapeutic endoscopy if they meet inclusion criteria. They will be asked to sign the informed consent form if they accept entering into the study.

### **Enrollment meeting**

Patients who are eligible for inclusion will receive both oral and written information about the study. The oral information will be delivered in a room only used for that purpose to avoid disturbances. The patient can be offered to have the enrollment meeting at his/her home. The investigator will have enough time to explain the content, extent, purpose, expected risks and advantages of the study in plain Danish or English. The patient will have enough time to read the written information and to ask questions. The following will be covered during the interview:

- The purpose and organization of the study
- The procedures during the therapeutic endoscopy
- The permission to access the patient's files to register any adverse reaction, medication use, blood tests and other clinical parameters perioperatively, and that this permission will also give the sponsor, the investigators, the Danish Medicines Agency, the GCP unit (Good clinical practice unit), and the Danish Data Protection Agency access to patient files during monitoring
- The methods used in the study
- The right to ask for additional information at all times
- The right of the patient to withdraw at any time during trial without explanation
- The insurance
- The contact person

At the end of the enrolment meeting the patient may sign the informed consent if they wish, and may also be given the time needed for consideration (at least 24 hours). The informed consent will be written in accordance with Danish law (see Annex III). Patients will be informed if any changes in the study occur, as this might influence the patient's willingness to participate or the safety of the participating patients. The approved document will be updated accordingly.

### **Intervention**

The intervention of the study will be according to the phase of the trial.

Phase I: Day 1, medical history, clinical examination and laboratory testing of the patient, as well as the pouchoscopy with biopsies to determine PDAI. During the same endoscopy, the study drug will be applied.

Phase II: Day 1, medical history, clinical examination and laboratory testing of the patient, as well as the pouchoscopy with biopsies to determine PDAI.

Day 1-7, patient is given the study drug combination as an enema daily for one week in the hospital, the first dose during endoscopy, to ensure correct administration and compliance.

### **Follow-up**

Follow-up will be:

- Phase I: Day 7 after the therapeutic endoscopy (Can be day 6-9)
- Phase II: Day 14 after the first diagnostic endoscopy (Can be day 13-16)

Follow-up will be a medical history, clinical examination of the patient, laboratory testing and a diagnostic endoscopy. Patients' pouchitis will be assessed according to the PDAI.

After the follow-up endoscopy, the patient will receive the standard treatment at Zealand University Hospital for acute pouchitis, which consists of oral metronidazole 500 mg x 3 for 10 days or ciprofloxacin 500 mg x 2 for 10 days. The type of treatment is decided on by the patient's gastroenterologist.

#### Final study visit

30 days after the follow-up, the patient will receive a telephone consultation. Patients will be asked about symptoms of pouchitis and if they had any adverse reactions or side effects to the treatment. See Appendix 8.

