### Phase I

Tolerability of the treatment is tested on 6 patients with a single dose of the combined medication applied endoscopically. See also appendix 14 for a flow-chart.

Patients will be identified by the treating gastroenterologist through the outpatient clinic when presenting with pouchitis and then informed in detail and screened according to the inclusion and exclusion criteria. The patient then gets at least 24 hours to reflect before signing the informed consent form to enter the trial.

- Day 1:
  - Clinical examination is performed and pre-treatment blood samples taken
  - Endoscopy with biopsies is performed and GM-CSF, metronidazole and fosfomycin is sprayed into the pouch as a single dose
- Day 7:
  - Clinical examination, post-treatment blood samples,
  - Endoscopy with biopsies
  - Recording of any adverse reactions or other adverse events (can be any day between day 6-9)
- Afterwards, the patient receives the standard treatment at Zealand University Hospital for acute pouchitis, consisting of a 10-day course of oral metronidazole 500 mg x 3 or ciprofloxacin 500 mg x 2.
- Day 30:
  - Telephone call to the patient to ask about symptoms of pouchitis and any side effects. (Can be any day between day 30 and 37).

After the last patient in phase I has had their 30 day follow-up, the safety and feasibility of the study drug application will be assessed by the sponsor and investigators of the study. If no serious adverse events of reactions occurred, the Phase II study will be initiated.

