## Phase II:

Depending on effect of the first study, this phase will comprise the treatment of 12 patients with a daily dose of the combined medication. The study drug will be applied in the hospital, to ensure the correct dosage and concentration. See also appendix 15 for a flow-chart.

Clinical and endoscopic control after 14 days with blood samples and biopsies. Patients who have been a part of the Phase I study, can be included if they fulfill inclusion criteria at time of inclusion for Phase II.

Inclusion will follow the procedures from the Phase I trial. Patients will be identified by the treating gastroenterologist through the outpatient clinic when presenting with pouchitis and then informed in detail and screened according to the inclusion and exclusion criteria. The patient then gets at least 24 hours of reflection time before signing the informed consent form to enter the trial.

- Day 1:
  - Clinical examination, blood samples
  - Endoscopy with biopsies and GM-CSF, fosfomycin and metronidazole applied in the pouch as a spray
- Day 2-7:
  - Enema with GM-CSF and metronidazole/fosfomycin applied in the hospital once daily
- Day 14:
  - Clinical examination, blood samples
  - Endoscopy with biopsies
  - Recording of any adverse reactions or other adverse events (Can be any day between day 13-16)
- Afterwards, the patient gets the standard treatment at Zealand University Hospital for acute pouchitis, which consisting of oral metronidazole 500 mg x 3 for 10 days or ciprofloxacin 500 mg x 2 for 10 days.
- Day 37:
  - Telephone call to the patient to ask for symptoms of pouchitis, any side effects. (Can be any day between day 37 and 44).

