#### Study procedure - evaluation

##### Clinical evaluations

At the first baseline visit, a thorough medical history will be taken both by using a patient interview as well as by using past medical records from the electronic health records. A list of current medications is made, where all currently taken medications should be included, both prescription and over-the-counter medicine, as well as medicine taken within the last 30 days. The patients PDAI score must be recorded.

The physical examination will include a measurement of vital signs (blood pressure, pulse, temperature, respiratory frequency), as well as cardiopulmonary, gastrointestinal and gross neurological examination. Current weight, height, BMI (body mass index), ASA score, performance status.

Subsequent visits will include a short update of the medical history, an update of the PDAI as well recording any adverse reactions during the study period. A clinical symptom-directed examination is done if the investigator deems this necessary.

All data is recorded in Easytrial by direct entry, using autoquery to minimize faulty data entry.

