#### **Safety assessments and adverse events or reactions**

An adverse event (AE) is any untoward medical occurrence in a patient or clinical investigation subject that has been given a pharmaceutical product, regardless of its causal relationship to the study treatment. This can be an abnormal laboratory finding, a symptom or disease coincident in time with the use of the investigational medicinal product.

During and after administration of GM-CSF, fosfomycin and metronidazole, any adverse events or intercurrent illnesses will be reported. Patients who have known allergy to GM-CSF, fosfomycin and or metronidazole are excluded from study participation. The administration of the study drug combination will be in the presence of a medical doctor, the principal investigator. Patients will be observed in the endoscopy unit for at least 1 hour after the first administration of the drug. In case of the occurrence of

an adverse event or serious adverse event, monitoring and further treatment steps will be taken according to the type and severity of reaction.

The severity of the AE will be assessed using the following grading system:

- Mild: requires minimal or no treatment, does not interfere with the patient's daily activities
- Moderate: low level of inconvenience or concern with therapeutic measures, some interference with the patient's daily activities
- Severe: interrupts a patient's daily activities, may require systemic drug therapy or other treatment, and is usually incapacitating
- Life threatening: places the patient at immediate risk of death from the reaction as it occurs

Changes in the severity of the AE will be documented.

All AEs, including both local and systemic events not meeting the criteria for 'serious adverse events' will be captured on the appropriate form for recording AEs. We will collect information on

- Description of the event
- Time of onset
- Clinician's assessment of the severity
- Relationship to the study product
- Time of resolution/stabilization of the event

Any medical condition that the patient has at baseline (time of inclusion in the study), will not be considered or reported as an AE. If an existing medical condition worsens during the study, it will be recorded as an AE.

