Appendix 8 – Follow-up Day 7/14/(30/37)

Name:

Side effects:		
GM-CSF  Fever  Myalgia  Malaise  Abdominal pain  Diarrhea  Rash  Chest pain  Weight loss  Nausea  Vomiting  Peripheral edema  Dyspnea  Hypoxemia  Hypotension  Tachycardia  Flushing  Metabolic disease  Hyperbilirubinemia  Cardiac dysrhythmia  Pharyngitis	Metronidazole  Nausea  Glossitis  Dry mouth  Dysgeusia  Stomatitis  Myalgia  Candida-infection  dark urine	Fosfomycin  Phlebitis  Vomiting  Abdominal pain  Diarrhea  Rash  Fatigue  Dysgeusia  Decreased appetite  Vertigo  Headache
Adverse reactions           		
Serious adverse reactions / Life-threatening adverse reactions  Capillary leak syndrome           		

Protocol code no: 2020-01-GMF-1  
EudraCT no: 2020-000609-10

Clinical PDAI to be filled in at follow-up:

Criteria	Score	Patient score
Clinical		
Stool frequency		
Usual postoperative stool frequency	0	
1-4 stools/day > than postoperative usual	1	
>3 stools/day > postoperative usual	2	
Rectal bleeding		
None or rare	0	
Present daily	1	
Fecal urgency or abdominal cramps		
None	0	
Occasional	1	
Usual	2	
Fever (temperature > 37.8)		
Absent	0	
Present	1	
Total	6	

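### The Day 30/37 safety call and its form use side-effect and reaction wording, with no cause-neutral question or entry for an unlisted or serious event, although the protocol requires all adverse events to be reported

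*Protocol*

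**What the plan says.** **The duty.** Section 7 (Safety assessments and adverse events or reactions) defines an adverse event "regardless of its causal relationship to the study treatment" and states: "During and after administration of GM-CSF, fosfomycin and metronidazole, any adverse events or intercurrent illnesses will be reported". It lists five items to collect per event: description, onset, severity, relationship and resolution. Under Adverse reactions, the study team then judges whether the event is related. Under Unexpected adverse event, both events and reactions are monitored to Day 30 (Phase I) or Day 37 (Phase II).

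**The decision.** Section 4, Phase I, has the sponsor and investigators assess safety after the last patient's 30-day follow-up. Phase II begins if no serious adverse events or reactions occurred (the text prints *of*, evidently for *or*).

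**The collection at the final contact.**
- Section 7, Final study visit: "Patients will be asked about symptoms of pouchitis and if they had any adverse reactions or side effects to the treatment", with a pointer to Appendix 8.
- Section 4, Phase I: "Telephone call to the patient to ask about symptoms of pouchitis and any side effects". Phase II: "Telephone call to the patient to ask for symptoms of pouchitis, any side effects".
- Section 7, Clinical evaluations, for visits after baseline: "an update of the PDAI as well recording any adverse reactions during the study period", plus a short history update.
- Appendix 2, both phases: the safety row is headed as an assessment of adverse reactions.
- Appendix 8: blocks for side effects, for adverse reactions, and for "Serious adverse reactions / Life-threatening adverse reactions".

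**The contrast.** For the Day 7 visit, section 4 has "Recording of any adverse reactions or other adverse events"; the Day 14 line in Phase II has the same scope.

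**The concern.** The protocol sets a sound order: collect every event first, then let the investigator decide which are reactions. At the last contact the question and the form start from the second step. An unlisted event that the patient does not connect with the study drug, such as an admission for something apparently unrelated, gets no direct question there, and the form has no entry that is neutral as to cause.

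The Phase I primary outcome is safety in six patients, so one event that goes unheard can change the result. The decision to start Phase II rests on serious events of any cause, and the Day 30 call is the last scheduled chance to learn of them.

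**Working it through.** No figure in the protocol is at stake, so the check is a comparison of texts, a count of form items and one illustration.

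**1. Scope, side by side**

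| Place | Scope |
|---|---|
| Section 7, safety assessments | Any event, whatever the cause |
| Section 4, Day 7 and Day 14 | Reactions and other adverse events |
| Section 4, start of Phase II | Serious events or reactions |
| Sections 4 and 7, Day 30/37 call | Pouchitis symptoms; side effects or reactions |
| Appendix 2, safety row | Reactions |
| Appendix 8 | Listed side effects; reactions; serious reactions |

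The wider wording is used at Day 7/14 and dropped at the final call. Appendix 8 serves both contacts.

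**2. What the Appendix 8 list covers**

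Pre-printed items: 20 (GM-CSF) + 8 (metronidazole) + 10 (fosfomycin) = 38. I compared them with the section 3 lists of known effects that will not be registered as adverse reactions. All 38 appear there; the only difference in degree is that section 3 says light headache and the form says headache. Apart from the capillary leak box among the serious reactions, the form prompts only for symptoms that, by the protocol's own rule, do not count as adverse reactions. A reaction that does count must enter through the reaction-worded question, a free entry under a reaction heading, or the patient's initiative.

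**3. The period concerned**

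By the nominal days in section 4, the interval from the follow-up visit to the call is 30 − 7 = 23 days in Phase I (23/30 = 77% of the window) and 37 − 14 = 23 days in Phase II (23/37 = 62%). The call is the only scheduled contact after that visit. These are calendar days, not shares of risk: dosing ends on Day 1 in Phase I and Day 7 in Phase II.

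**4. Direction of the effect on the Phase II decision (illustration)**

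Let p be the true risk of a serious event per Phase I patient and s the share of all such events, including those found at Day 7, that become known. With 6 patients,

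P(no serious event known) = (1 − p·s)^6.

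| p (assumed) | s = 100% | s = 75% | s = 50% |
|---|---|---|---|
| 5% | 73.5% | 79.5% | 85.9% |
| 10% | 53.1% | 62.6% | 73.5% |
| 20% | 26.2% | 37.7% | 53.1% |

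For example, p = 10% and s = 75% gives (1 − 0.075)^6 = 0.626. Neither p nor s is given in the protocol. The table shows only that under-capture makes a decision to proceed more likely.

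**The case against.** The strongest reply is that the final call is not the only channel, and that for many symptoms it is not causally worded in practice.

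- Final study visit sends the caller to Appendix 8, and section 7 (Unexpected adverse event) says patients are asked whether they developed the events on that form. Saying whether one had fever or chest pain needs no causal judgement. This stands for the listed items.
- The same section lets patients telephone throughout about any event or reaction. This stands, but it relies on the patient's initiative.
- Appendix 2 has concomitant medicines reviewed at Day 30/37, which can reveal an illness that led to a new medicine. This stands in part. The history update under Clinical evaluations may also apply, although Appendix 2 marks no medical history at that contact. Consent allows access to health records, but no review is scheduled at the call.
- Section 7 refers to an appropriate form for adverse events and another for serious ones. It would therefore be wrong to infer that onset, severity, relationship and resolution go uncollected. But section 9 names only Appendices 3–6 and 8 as source forms, and none of them is an adverse-event form.
- Section 7 treats all serious events as related, so once known they would fit the serious-reaction entry. Knowing of them is the difficulty.
- Section 3 measures Phase I safety by adverse reactions, so the wording matches that outcome. But reactions are to be derived from events, and the Phase II decision uses events.

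A reader might infer that the patient decides causality, or that later events reach the investigator only if the patient blames the treatment. The protocol supports neither: the study team judges causality, and the routes above are open. Nor would it be right to apply a patient-attribution filter to all Phase I reactions from Day 1, because the Day 7 visit also records other events.

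**Conclusion.** The point holds in limited form. The Day 30/37 question, the Appendix 2 row and the Appendix 8 headings are narrower than the duty to report all adverse events and, for Phase I, narrower than the serious-event condition for starting Phase II. The exposed events are those not on the Appendix 8 list, mainly those arising after Day 7/14. They carry weight because the listed items are excluded from registration as adverse reactions. This rests on reading the call as worded; an interviewer who asks more broadly would close part of the gap, but the protocol does not require it. The size of any under-capture cannot be derived from the protocol. Its direction is towards fewer recorded events and an easier decision to proceed. The consequence for that decision concerns the Phase I call only.

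**What to change.** 1. In section 4 (Day 30 and Day 37) and section 7 (Final study visit, Clinical evaluations), ask about any new or worsened symptom, illness or hospital contact since the last visit, whatever the cause. Keep the Appendix 8 list as a supplement.
2. Rename the Appendix 2 row *Assessment of adverse events* in both phases.
3. Add adverse-event and serious-adverse-event entries to Appendix 8 with the five items that section 7 requires, or name the separate form that holds them and list it among the source forms in section 9.
4. State that adverse reactions are derived from these entries afterwards, by the investigator's causality judgement under section 7, Adverse reactions.

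The cost is a few changed sentences, one row heading and one form page, with no added visit or procedure. Somewhat more unrelated events will be recorded and will need assessment.
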